34. Use of any drugs or substances, including herbal treatments, such as fluoxetine, fluvoxamine, aspirin, norethisterone, rifampicin, etc that are known to be substrates, inducers, or inhibitors of CYP2C19 within 4 weeks before the first administration of study drug.
35. Subjects under judicial supervision, guardianship, or curatorship.
36. Poor venous access for blood sampling.
37. Subjects who are intolerant to sucrose.
38. Previous exposure to balovaptan.

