#### **4.1.1 Inclusion Criteria**

Subjects must meet the following criteria for study entry:

1. Healthy male and female subjects, aged 18 to 65 years, inclusive. Healthy status is defined by absence of evidence of any active or chronic disease following a detailed medical and surgical history, a complete physical examination including vital signs, 12-lead ECGs, hematology, blood chemistry, urinalysis, and serology.
2. Body mass index (BMI) between 18 and 32 kg/m^2 inclusive, at screening.
3. For women of childbearing potential: if engaging in heterosexual activity, agreement to use at least two adequate forms of contraception during the entire study and for 90 days following the last dose of study drug. Contraceptive measures are not required for women with exclusively same-sex partners and for those for whom complete abstinence is their preferred and usual lifestyle.

- a. A woman is considered to be of childbearing potential if she is postmenarchal, has not reached a postmenopausal state (> 12 continuous months of amenorrhea with no identified cause other than menopause, confirmed with follicle-stimulating hormone (FSH)  $\geq 35$  IU/L), and has not undergone surgical sterilization (removal of ovaries and/or uterus).
  - b. The following are adequate contraceptive methods: bilateral tubal ligation; sterilization of male partner; hormonal contraceptives; hormone-releasing intrauterine devices; copper intrauterine devices; Essure.
  - c. Barrier methods alone are not considered an adequate form of contraception for this study and if utilized must be supplemented by one of the adequate methods described above. For this study barrier contraception methods are defined as: male or female condom with or without spermicide (male and female condom must not be used simultaneously); and cap, diaphragm, or sponge with spermicide.
  - d. Hormonal contraceptive methods must be supplemented by a barrier method.
4. For men: agreement to use contraceptive measures, and agreement to refrain from donating sperm, as defined below:
    - a. With female partners of childbearing potential or pregnant female partners, men must remain abstinent or use a condom during sexual activity for the entire study and for 90 days after the last dose of study drug to avoid exposing the embryo. Men must refrain from donating sperm during this same period.
  5. Able to participate, and willing to give written informed consent and to comply with the study restrictions.

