26. Any donation of blood or plasma or significant blood loss within 3 months prior to screening.
27. Dietary restrictions that would prohibit the consumption of standardized meals or the high-fat, high-calorie meal planned for this study.
28. Use of any prohibited medications or food before study start or subjects who do not agree to refrain from consuming prohibited medications or food during the study.
29. Subjects likely to need concomitant medication during the study (including for dental conditions).
30. Subjects who have received any prescribed systemic or topical medication within 4 weeks (or within 5 times the elimination half-life of the medication, whichever is longer) of the first administration of study drug, unless in the opinion of the Investigator the medication will not interfere with the study procedures or compromise safety, and subjects who have received slow release medicinal formulations considered to still be active within 4 weeks (or within 5 times the elimination half-life of the medication, whichever is longer) of the first administration of study drug will also be excluded unless in the opinion of the Investigator the medication will not interfere with the study procedures or compromise safety.
31. Used the following within 7 days before the first study drug administration, unless in the opinion of the Investigator the medication will not interfere with the study procedures or compromise safety:
  - any nonprescribed systemic or topical medication
  - herbal remedies

Paracetamol (up to 4 g/day within 7 days before study drug administration and 2 g/day within 48 hours before study drug administration), dietary supplements, vitamins and minerals, hormonal contraceptives, and hormone replacement therapy are allowed.

32. Received any medications known to chronically alter drug absorption or elimination processes within 4 weeks before the first administration of study drug, unless in the opinion of the Investigator the medication will not interfere with the study procedures or compromise safety.
33. Use of any drugs or substances, including herbal treatments such as St John's wort, that are known to be substrates, inducers, or inhibitors of CYP3A4 within 4 weeks before the first administration of study drug.

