34. Use of any drugs or substances, including herbal treatments, such as fluoxetine, fluvoxamine, aspirin, norethisterone, rifampicin, etc that are known to be substrates, inducers, or inhibitors of CYP2C19 within 4 weeks before the first administration of study drug.
35. Subjects under judicial supervision, guardianship, or curatorship.
36. Poor venous access for blood sampling.
37. Subjects who are intolerant to sucrose.
38. Previous exposure to balovaptan.

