##### **4.4.1 Permitted Therapy**

Existing hormonal contraceptives and hormone replacement therapy regimens may remain unchanged during the conduct of the study.

Acetaminophen/paracetamol is allowed up to a maximum dose of 4 g/day within 7 days before study drug administration and 2 g/day within 48 hours before study drug administration, but total should not exceed 4 g during the week prior to dosing. Subjects will be instructed not to exceed these limits.

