#### **4.4.2 Prohibited Therapy**

Participation in an investigational drug study within 4 weeks or 5 times the elimination half-life, whichever is longer, prior to first dosing, or within 5 months prior to first dosing in case of a study with a biologic, as calculated from the day of follow-up from the previous study. Participation in an investigational device study within 4 weeks prior to first dosing is prohibited.

Any prescribed systemic or topical medication is prohibited within 4 weeks (or within 5 times the elimination half-life of the medication, whichever is longer) of the first dose administration, unless in the opinion of the Investigator the medication will not interfere with the study procedures or compromise safety, and slow release medicinal formulations considered to still be active within 4 weeks (or within 5 times the elimination half-life of the medication, whichever is longer) of the first dose administration are also prohibited unless in the opinion of the Investigator the medication will not interfere with the study procedures or compromise safety.

The following concomitant medications in particular are prohibited, unless an exception has been agreed as mentioned above.

- P-gp substrates
- Any inhibitor of CYP3A or CYP2C19 taken within 4 weeks (i.e. more than 5 half-lives) prior to study drug administration, including but not limited to the following drugs: ketoconazole, miconazole, itraconazole, erythromycin, clarithromycin, ranitidine, cimetidine, fluoxetine, fluconazole, fluvoxamine, until follow-up.

Any inducer of CYP3A or CYP2C19 taken within 4 weeks prior to study drug administration, including but not limited to the following drugs: rifampicin, rifabutin, glucocorticoids, carbamazepine, phenytoin, phenobarbital, and St. John's wort, until follow-up. Use of any nonprescribed systemic or topical medication or herbal remedies within 7 days before the first study drug administration through follow-up is prohibited, unless in the opinion of the Investigator the medication will not interfere with the study procedures or compromise safety.

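### Does exclusion 34's naming of norethisterone conflict with the permission for hormonal contraceptives and HRT in a way that requires a change to the plan?

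*Combined protocol and SAP*

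**What the plan says.** **The restrictive passages.** Exclusion 34 (Section 4.1.2) names norethisterone among the CYP2C19 agents barred before first dosing: drugs "such as fluoxetine, fluvoxamine, aspirin, norethisterone, rifampicin, etc that are known to be substrates, inducers, or inhibitors of CYP2C19 within 4 weeks before" the first dose of study drug. The synopsis names the same agents: "such as fluoxetine, fluvoxamine, aspirin, norethisterone, rifampicin, etc that are known to be substrates, inducers, or inhibitors of CYP2C19". Exclusion 33 has the same structure for agents "that are known to be substrates, inducers, or inhibitors of CYP3A4 within 4 weeks before the first administration of study drug". Exclusions 30 to 32 let the investigator judge that a medication will not interfere; 33 and 34 do not.

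**The permissive passages.**
- Inclusion 3b (Section 4.1.1) lists as adequate methods "bilateral tubal ligation; sterilization of male partner; hormonal contraceptives; hormone-releasing intrauterine devices; copper intrauterine devices" and one further device. Inclusion 3d requires a barrier method alongside hormonal ones.
- The note under exclusion 31 says that, among other things, "hormonal contraceptives, and hormone replacement therapy are allowed".
- Section 4.4.1 says: "Existing hormonal contraceptives and hormone replacement therapy regimens may remain unchanged during the conduct of the study".
- Exclusion 22 bars women on HRT only where postmenopausal status cannot be established, which implies that other HRT users may enter.

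**The on-study list.** Section 4.4.2 opens its list with "The following concomitant medications in particular are prohibited, unless an exception has been agreed as mentioned above". It covers P-gp substrates and CYP3A or CYP2C19 inhibitors until follow-up, and then "Any inducer of CYP3A or CYP2C19 taken within 4 weeks prior to study drug administration", also until follow-up. It lists no CYP substrates and does not name norethisterone.

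**The rules that decide.** Section 4.1.2 excludes anyone who meets any listed criterion. Section 4.2 gives a randomization number only to subjects who meet all eligibility criteria. Section 9.2 disallows eligibility waivers. Section 6.6 removes from the PK population subjects with significant eligibility violations, with reasons documented and decisions made before database lock.

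**The concern.** Norethisterone is a progestin. If it is in a woman's contraceptive or HRT product, Section 4.4.1 and the note under exclusion 31 appear to welcome her and exclusion 34 turns her away. Neither side refers to the other. Exclusion 34 also ends its list openly and does not say whether norethisterone is there as a substrate, an inducer or an inhibitor. It is therefore unclear whether the on-study list in Section 4.4.2, which omits CYP substrates, would reach it. For other hormonal products the documents give no CYP status at all.

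Two things could be at stake. Screening staff might decide the same case differently. And if such a woman were enrolled, Section 6.6 does not say whether her product would count as a significant violation. In an open-label study, with exclusions required only before database lock, that decision could be made after concentrations are known. With a target of 12 evaluable subjects, each such decision could matter.

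**Working it through.** No figure in the plan rests on this wording, so the check is mainly a reading of the passages against one another.

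**1. What each passage governs.**

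| Place | Question it answers | Excepts norethisterone? |
|---|---|---|
| Inclusion 3b/3d | Which methods count as adequate contraception | No |
| Note under exclusion 31 | What is tolerated alongside that item's 7-day rule on nonprescribed and herbal products | No |
| Section 4.4.1 | What an enrolled subject may keep taking during the study | No |
| Exclusion 22 | Whether menopausal status can be established in HRT users | Not addressed |
| Exclusion 34 | Which CYP2C19 agents bar entry | Bars it by name |

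The first four do not say that satisfying them overrides another exclusion. Contraception can be adequate under inclusion 3b and the subject still fail a different criterion.

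**2. The literal outcome for a norethisterone user.** She meets exclusion 34. Section 4.1.2 excludes a subject on any one criterion, Section 4.2 then gives her no randomization number, and Section 9.2 closes the waiver route. The result is a screening failure. The on-study question under Sections 4.4.1 and 4.4.2 does not arise for her, because she is never on study.

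**3. How many subjects could be concerned.**
- Planned women: 16 × 0.5 = 8.
- Minimum of either sex: 16 × 0.3 = 4.8, so 5. Women therefore range from 5 to 16 − 5 = 11.

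These are counts of women, not of women affected. The share using hormonal or norethisterone-containing products is not given, so the affected number cannot be computed.

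**4. Effect on evaluable numbers and precision.** A woman excluded at screening is not one of the 16 enrolled. If one were enrolled and later removed from the PK population, there is room for 16 − 12 = 4 losses before the target is missed, and Section 4.1 allows subjects who withdraw to be replaced. The plan's precision figure reproduces, using a residual CV of 14% and 10 degrees of freedom for two sequences of 6 subjects:
- σ = √ln(1 + 0.14²) = 0.1393
- factor = exp(t(0.95, 10) × 0.1393 × √(2/12)) = 1.109, against the stated 1.11.

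Nothing in the eligibility wording enters that calculation.

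**5. Effect on the estimates.** Both primary comparisons are within subject (Section 3.3). If a woman on an unchanged regimen were enrolled, she would take it in the test and reference periods alike. On the log scale an effect common to both periods cancels from her own contrast. This assumes that the effect is constant across periods; the documents give no data on it.

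**The case for a change.** The best case for a change is that the conflict is on the page and cheap to remove. Norethisterone is named, so no view on its CYP status is needed. Section 4.4.1 speaks of existing regimens, which normally fall within the 4 weeks before dosing, and it carries no limit of the kind that can be read into the note under exclusion 31. The protocol states no order of precedence between a specific bar and a general permission. Section 4.4.2 adds a further version of the restriction with its own exception route. One sentence in the protocol and one in Section 6.6 would settle it.

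Much of this stands as a comment on drafting: the passages do not refer to each other, and Section 4.4.2 is not aligned with exclusions 33 and 34. It does not show that the result is undetermined. No precedence rule is needed where any single exclusion is enough to bar entry. The point about other hormonal products shows only that the documents are silent on their CYP status.

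The database-lock point is general to open-label PK studies and is not created by this wording. Section 6.6 already limits removal to significant violations with documented reasons, and Section 6 calls for an analysis plan finalized before lock, where the classification can be written down in the ordinary way. This is a single-center study, so a query from one screening team would settle a doubtful case before randomization.

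**Conclusion.** The tension in wording is real, but it is a drafting gap that screening staff and analysts can close from the text itself. Read literally, exclusion 34 bars entry and the permissive passages apply to those who pass it. Both food-effect and esomeprazole comparisons remain sound within-subject contrasts. No number affected, bias, evaluable-subject shortfall or loss of precision has been shown, and clearer wording would not alter any result or conclusion.

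This rests on two assumptions: that norethisterone is a component of some contraceptive or HRT products, which the documents do not say, and that Section 4.1.2's any-criterion rule is applied as written. The inconsistent passages should be reconciled when the protocol is next edited, with the sponsor's clinical team deciding which rule is intended. That is a clerical matter and does not call for a change to the statistical plan.

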## **4.2 METHOD OF TREATMENT ASSIGNMENT AND BLINDING**

This is a single-center, part-randomized, open-label, 3-treatment, 3-period crossover study. Subjects will be randomly assigned in equal proportions to one of the 2 treatment sequences according to a computer-generated randomization scheme.

After informed consent is obtained, subjects will be screened according to the inclusion and exclusion criteria. Subjects who have met all eligibility criteria will receive a randomization number on Day 1 of the first treatment period and according to the randomization code generated by the Biostatistics Department of PRA Health Sciences (PRA). Replacement subjects will receive the randomization number of the subject to be replaced, increased by a fixed unit (e.g., 1901 replacement number for randomization number 1001), and will be assigned to the same treatment sequence.

Subjects who drop out or withdraw for any reason without completing all screening evaluations successfully, will be considered "screening failures." Such subjects will not receive a randomization number, and only applicable data will be entered in the electronic case report forms (eCRFs).

### **4.2.1 Blinding**

Not applicable; this is an open-label study.

### **4.3 STUDY TREATMENT AND OTHER TREATMENTS RELEVANT TO THE STUDY DESIGN**

The investigational medicinal products (IMPs) for this study are balovaptan and esomeprazole.

#### **4.3.1 Study Treatment Formulation, Packaging, and Handling**

##### **4.3.1.1 Balovaptan**

Balovaptan 20-mg dispersible tablets (Ro 528-5119/F41) will be supplied by the Sponsor in high-density polyethylene bottles. Balovaptan must be stored and handled according to the details specified on the product label. For additional details, refer to the balovaptan IB.

##### **4.3.1.2 Esomeprazole**

Esomeprazole 40-mg capsules will be obtained commercially by the site. Esomeprazole must be stored and handled according to the specifications in the US package insert (USPI).

#### **4.3.2 Study Treatment Dosage, Administration, and Compliance**

The treatment regimens are summarized in Section [3.1](#)

Refer to the balovaptan Investigator Brochure or esomeprazole USPI for detailed instructions on drug preparation, storage, and administration.

Cases of accidental overdose or medication error along with any associated adverse events, should be reported as described in Section [5.4.4](#).

Guidelines for treatment interruption or discontinuation of subjects who experience adverse events are provided in Section [5.1](#).

##### **4.3.2.1 Balovaptan**

Single oral doses of balovaptan 20 mg (1 × 20 mg tablet) will be administered following consumption of a high-fat, high-calorie meal (Treatment A), after a ≥ 10 h fast (Treatment B), and following a ≥ 10 h fast and coadministered with esomeprazole 40 mg (Treatment C) in a fasted state. Balovaptan will be administered with approximately 240 mL of water.

For the fed treatment, balovaptan will be administered within 30 minutes of the start of the meal and after all of the meal has been consumed.

For fasted treatments, subjects are to continue to fast for 4 hours following dosing and refrain from drinking for 1 hour prior to and 1 hour after balovaptan administration, except for water provided to take study medication.

#### **4.3.2.2 Esomeprazole**

Single doses of esomeprazole 40 mg will be administered alone for 4 days prior to coadministration with balovaptan 20 mg on Day 1 of Period 3, and administered alone on Day 2 of Period 3. When esomeprazole is coadministered with balovaptan, esomeprazole will be administered 1 hour prior to balovaptan in a fasted state. Esomeprazole will be administered with approximately 240 mL of water.

#### **4.3.3 Investigational Medicinal Product Accountability**

Balovaptan will be provided by the Sponsor. Esomeprazole will be procured by the study site. The study site will acknowledge receipt of balovaptan by returning to the Sponsor the appropriate documentation form to confirm the shipment condition and content. Esomeprazole shipping documents will be filed at the site. Any damaged shipments will be replaced.

Balovaptan will either be disposed of at the study site according to the study site's institutional standard operating procedures (SOPs) or be returned to the Sponsor with the appropriate documentation. The site's method of destroying Sponsor-supplied IMPs must be agreed to by the Sponsor. The site must obtain written authorization from the Sponsor before any Sponsor-supplied IMP is destroyed, and IMP destruction must be documented on the appropriate form. Esomeprazole will be disposed of at the study site according to the study site's institutional SOPs.

Accurate records of all IMPs received at, dispensed from, returned to, and disposed of by the study site should be recorded on the Drug Inventory Log.

#### **4.4 CONCOMITANT THERAPY, PROHIBITED FOOD, AND ADDITIONAL RESTRICTIONS**

Concomitant therapy consists of any medication (e.g., prescription drugs, over-the-counter drugs, vaccines, or homeopathic remedies, nutritional supplements) used by a subject in addition to protocol-mandated treatment from 4 weeks prior to initiation of study drug to the study completion/ discontinuation visit. All such medications should be reported to the Investigator or designee and recorded on the Concomitant Medications eCRF.

##### **4.4.1 Permitted Therapy**

Existing hormonal contraceptives and hormone replacement therapy regimens may remain unchanged during the conduct of the study.

Acetaminophen/paracetamol is allowed up to a maximum dose of 4 g/day within 7 days before study drug administration and 2 g/day within 48 hours before study drug administration, but total should not exceed 4 g during the week prior to dosing. Subjects will be instructed not to exceed these limits.

#### **4.4.2 Prohibited Therapy**

Participation in an investigational drug study within 4 weeks or 5 times the elimination half-life, whichever is longer, prior to first dosing, or within 5 months prior to first dosing in case of a study with a biologic, as calculated from the day of follow-up from the previous study. Participation in an investigational device study within 4 weeks prior to first dosing is prohibited.

Any prescribed systemic or topical medication is prohibited within 4 weeks (or within 5 times the elimination half-life of the medication, whichever is longer) of the first dose administration, unless in the opinion of the Investigator the medication will not interfere with the study procedures or compromise safety, and slow release medicinal formulations considered to still be active within 4 weeks (or within 5 times the elimination half-life of the medication, whichever is longer) of the first dose administration are also prohibited unless in the opinion of the Investigator the medication will not interfere with the study procedures or compromise safety.

The following concomitant medications in particular are prohibited, unless an exception has been agreed as mentioned above.

- P-gp substrates
- Any inhibitor of CYP3A or CYP2C19 taken within 4 weeks (i.e. more than 5 half-lives) prior to study drug administration, including but not limited to the following drugs: ketoconazole, miconazole, itraconazole, erythromycin, clarithromycin, ranitidine, cimetidine, fluoxetine, fluconazole, fluvoxamine, until follow-up.

Any inducer of CYP3A or CYP2C19 taken within 4 weeks prior to study drug administration, including but not limited to the following drugs: rifampicin, rifabutin, glucocorticoids, carbamazepine, phenytoin, phenobarbital, and St. John's wort, until follow-up. Use of any nonprescribed systemic or topical medication or herbal remedies within 7 days before the first study drug administration through follow-up is prohibited, unless in the opinion of the Investigator the medication will not interfere with the study procedures or compromise safety.

